## Test protocols

### Rate of Torque Development

Rate of force development is defined as a change in force over time (Newtons per second). To make the measurement more applicable in a group with diversity in gender, age and size, the length of the lever arm is considered, by measuring from the lateral joint space in the knee, to two centimetres above the lateral malleolus. Rate of torque development is denoted as Newton per meters per second per kilograms of bodyweight (Nm/s/kg).

A reliability study from 2019 showed that a fixated handheld dynamometer, a MicroFet 2 (Hoggan, Scientific L.L.C., Salt Lake City, USA) with a sampling rate of 100hz, has a good intra-tester reliability, and an acceptable measurement error (SEM  $\leq$ 15.5%).

### Knee flexion

The participant is lying prone, with hip in neutral position,  $0^\circ$ . The knee is flexed about  $20^\circ$ , with the leg resting on the testers fist wedged between the examination table and the ankle. The participant will be instructed to hold onto the side of the examination table. A strap fixated to the floor, is used to fixate the handheld dynamometer. The dynamometer is placed central to the line of lever demarcation, approximately 2cm proximal to the lateral malleolus.

### Knee extension

The participant is sitting with  $90^\circ$  hip flexion, knee flexed approximately  $60^\circ$ , with test leg resting in testers hand, and feet free of the floor. They will be instructed to hold onto the back of the examination table and keep their upper body upright. A strap fixated to the bottom of the examination bed, is used to fixate the handheld dynamometer anteriorly on the shin, corresponding to the line of lever demarcation. If the participant feels the metal of the gauge on their shinbone through the padding of the dynamometer, extra padding will be placed on the shin.

The participant will be instructed to *press against the dynamometer as fast and hard as possible, and to keep pushing until instructed to relax* (approximately 3-4sec.). Standardized verbal instruction is provided before each trial by the tester: *3-2-1-go-push-push-push and relax*. For the knee flexion, the participant will be instructed to bend their knee, and for the extension, to straighten the leg.

Participants will perform two test trials: one at 50% of self-estimated maximal force, and one at 100%. The assessor will hold the leg in starting position to allow full rest between trials, lasting 1-minute. Three maximal attempts are recorded. One tester will hold the dynamometer and instruct the patient (HS), while one tester (JL) manage data collection software (Hoggan Health Industries 2000, version 11.0.1, Quest Medical Group, Inc.). The order of the movements is decided by coin

toss. The affected leg is tested first in each movement. In the control group the affected leg will be decided by coin toss before tester HS enters the room.

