## Methods

The study design and analysis strategy have been published along with a trial registration (ClinicalTrials.gov NCT05789095). The study will include 13 adolescent participants with Osgood-Schlatter and a group of 13 pain free controls matched on sex, age, and sports participation on the group level. Testing will include bilateral rate of torque development measurements of knee extension and flexion, with a fixated handheld dynamometer, during a single test-session lasting approximately two hours. The examiner responsible for strength-testing will be blinded to case-status. Along with anthropometric data, participants will perform the anterior knee pain provocation test to assess pain-response to sustained knee loading, a countermovement jump test to assess power and jump height, and provide patient-reported measures of condition severity, pain, disability, and quality of life. Data collection will start February 2023 and is expected to be completed by May 2023.

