#### Clinical examination and treatment

The study procedures will be conducted by two examiners (JL and HS). JL will be aware of the case status and conducts the screening and preliminary testing. To avoid bias, examiner HS will be blinded for the case status during trial and will not know the Numerical pain Rating Scale-scores (NRS, 0-10, 'no pain' to 'worst pain imaginable') of the participants during testing. To strengthen the inter-reliability, the examiners will not change roles during the study.

The session starts with JL examining the potential participant in the OSD-case group, for Osgood-Schlatter. If the Osgood-Schlatter diagnosis is made, the participant is then enrolled. For the potential participant in the control group, JL screens for potential injury or pain in relation to the knee joint. In the absence of relevant pathology, the control-participant is enrolled.

Then, JL measures length of the lever arm and variables for peak hight velocity assessment. Participants will then answer the patient-reported outcome measures together with their parent/guardian.

For the rate of force development tests, HS will enter the room and conduct the tests as described below. For each attempt the participant will write down their NRS-rating on a piece of paper, out of sight from HS.

Before the rate of force development test is conducted, the participants are told that they can always abort the test, if they perceive that pain rises to such a degree that they can't continue the

testing, or they start feeling fearful or uncertain of their symptoms. They are ultimately told that potential pain felt during testing are not harmful and will subside within 24 hours, as is our experience from multiple earlier conducted tests.

HS leaves the room, for JL to conduct the Anterior Knee Pain Provocation test and save the NRS results.

HS returns to conduct the Counter Movement Jump Test, again blinded for the participants NRS-scores, which are written down on a piece of paper. HS leaves the room, and JL either treats the patient (case-group) or hands out compensation for participating (control-group).

Cases and controls will be instructed not to take any pain medication 24 hours prior to any assessment to ensure that this does not affect measurements.

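### The stated blinding covers administration of the strength test but not the capture and derivation of RTD, where the examiner who knows case status runs the software and no masking is described.

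*Combined protocol and SAP*

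**What the plan says.** The summary's Methods section states: "The examiner responsible for strength-testing will be blinded to case-status". Clinical examination and treatment divides the work between two examiners. One "will be aware of the case status and conducts the screening and preliminary testing". The other "will be blinded for the case status during trial and will not know the Numerical pain Rating Scale-scores". The same section fixes this for the whole study: "the examiners will not change roles during the study".

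The Knee extension section says how they work together during the RTD test. "One tester will hold the dynamometer and instruct the patient" describes the blinded examiner. The examiner who knows case status is there to "manage data collection software". On the yield of each test it says: "Three maximal attempts are recorded".

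Under Outcome measures, the force rate in N/s is multiplied by lever length and divided by body weight. The case-aware examiner measures the lever arm. Sample size names early RTD at 0-100 ms as the primary measure. Risks and adverse events removes a participant's data if case status becomes known to the blinded examiner, because of the risk of bias.

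**The concern.** Early RTD is not read directly from a dial. Someone or something must capture the trace, decide where force begins, and carry one or more of three attempts forward. The plan blinds the person at the participant's leg. It leaves the person at the software unblinded for all 26 participants and describes no masking of what follows. The hypotheses are directional, with lower RTD expected in cases, so any expectation would have a direction.

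The plan's own rule shows how seriously it takes this: loss of blinding in the tester is grounds to exclude data. No comparable protection is described for the capture and derivation of the same measurement. What is at stake is whether a reader can rely on blinding for the primary between-group comparison or only for the way the test was given.

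**Working it through.** **1. The plan's own figure.** Inputs from Sample size: means 6 and 3 Nm/kg/s (difference 3), SD 2.6, two-sided alpha 5%, power 80%. The standardised difference is 3/2.6 = 1.154. The two-sample t-test (noncentral t) gives n = 12.83, rounded up to 13 per group; power at 13 is 80.6%. The stated 13 reproduces, and masking would not change it.

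**2. Coverage of blinding, step by step.**

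| Step | Who, according to the plan | Blinded? |
|---|---|---|
| Lever arm measurement | Case-aware examiner | No |
| Holding dynamometer, instruction | Blinded examiner | Yes |
| Pain score per attempt | Participant, in writing, out of the blinded examiner's sight | Concealed from the blinded examiner |
| Data collection software | Case-aware examiner | No |
| Onset and RTD extraction | Not stated | Not stated |
| Choice or combination of three RTD attempts | Not stated (a mean of three is stated only for the jump test) | Not stated |
| Statistical analysis | Not stated | Not stated |

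**3. How sensitive one trial is to onset.** The plan describes the dynamometer "with a sampling rate of 100hz" when citing its reliability study; I assume the same rate applies here. One sample is then 1000/100 = 10 ms, a tenth of the 0-100 ms window. The documents give no force curves, so the following shape is an assumption: F(t) = (1 - exp(-t/tau))^k, with tau = 60, 80 or 120 ms and k = 1, 2 or 3.

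- Correct onset: RTD = F(100)/100.
- Onset 10 ms early: RTD = F(90)/100.
- Onset 10 ms late: RTD = [F(110) - F(10)]/100.

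| k | tau (ms) | Early onset | Late onset |
|---|---|---|---|
| 1 | 60 | -4.2% | -15.4% |
| 1 | 80 | -5.3% | -11.8% |
| 1 | 120 | -6.7% | -8.0% |
| 2 | 60 | -8.3% | +3.7% |
| 2 | 80 | -10.4% | +6.9% |
| 2 | 120 | -12.9% | +10.7% |
| 3 | 60 | -12.1% | +10.4% |
| 3 | 80 | -15.2% | +14.4% |
| 3 | 120 | -18.7% | +19.3% |

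The absolute change runs from 3.7% to 19.3%. The direction depends on the curve: with k = 1 both errors lower RTD, while with k = 2 or 3 late onset raises it.

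**4. What it would take to matter between groups.** The same error in both groups is not a source of differential bias in this sense. For an upper illustration, suppose every attempt in one group were shifted a full sample in one direction and none in the other.

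- On the planned case mean of 3: 0.037 x 3 = 0.11 to 0.193 x 3 = 0.58 Nm/kg/s, or 4-19% of the planned difference. With no true difference, SD 2.6 and 13 per group, p < 0.05 would occur in about 5.1% to 8.5% of studies, against 5%.
- On the planned control mean of 6: 0.037 x 6 = 0.22 to 0.193 x 6 = 1.16 Nm/kg/s. The top of that range gives about 19%, but needs the most extreme assumed curve and wholly one-sided handling.

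**The case against.** The strongest reply has four parts.

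**The blinding protects the part most open to influence.** Effort depends on instruction and encouragement, and the examiner giving both is blinded. The wording is standardised and the dynamometer is strapped in place. This stands: a reader might infer that blinding does nothing for the primary outcome, and the documents do not support that.

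**The roles are disclosed.** The summary claims blinding only for the strength-testing examiner, and the later sections openly give the software to the other one. This also stands. A reader might infer that the plan misrepresents its blinding; it does not. The summary alone is merely easy to read too broadly.

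**The mechanism is inferred.** The plan says nothing of discarding or repeating attempts, or of placing onset by hand. A reader might take the operator's role to include these, but the text says only that the software is managed and three attempts are recorded. If onset is automatic, the arithmetic on onset falls away and what remains is capture and the handling of attempts. The plan also promises to share its R code and full data set, which would help afterwards if raw curves are included.

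**Part of this is a specification gap.** A missing onset rule and a missing rule for combining attempts would be faults whoever was blinded. That is fair, and a fixed algorithm would remove much of the concern. It would not mask the files or the merge with case status.

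What survives is that a case-aware person has a stated, fixed role in producing the primary measure, and no masking is described from there on.

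**Conclusion.** The point holds in limited form. Blinding covers how the strength test is given and keeps pain scores from the examiner giving it. It does not cover how RTD is captured, and nothing available shows that it covers extraction or analysis.

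A reader might go further and conclude that the primary comparison is biased towards lower RTD in cases. The documents do not support that: they do not say who extracts RTD or how onset is set, and nothing shows handling that differs by group. The 4-19% figure is a per-trial sensitivity on assumed curves, not an estimate of bias, and the false-positive figures assume wholly one-sided handling. This is a low-cost improvement to the primary measure and does not affect the sample size. Some administrative pages were not in the copy reviewed, so a masking statement there cannot be excluded.

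**What to change.** - **Knee extension (and the same for flexion):** save all three maximal attempts for every participant under a coded ID that does not reveal group.
- **Outcome measures and Statistical methods:** have the already-blinded examiner, or an analyst without the case key, extract RTD from the coded files. Apply one fixed onset algorithm to every file, and lock the RTD data set before case status is merged.
- **Summary, Methods:** state that blinding applies to the examiner administering the test and that the software operator is not blinded.

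The cost is coding the files, a lock step and slightly later processing. No extra staff, equipment or visits are needed, and no second blinded operator is asked for. If raw curves have been saved, masked extraction can still be done after data collection.

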## Aim

To investigate if early and peak rate of torque development during knee extension is reduced in the asymptomatic limbs or during knee flexion in adolescents with Osgood-Schlatter, compared to a matched group of asymptomatic adolescents.

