## Expected results and implications

As the condition affects the knee-extensor mechanism, we expect lower levels of rate of torque development in the affected knee during extension. The main interest, however, is if the level of rate of torque development is also significantly reduced in non-symptomatic limbs or in knee flexion, in cases compared to symptom-free healthy controls. This would indicate inhibited neuromuscular function on a central level, due to other factors than local tissue pathology, such as pain chronicity, central muscle inhibition, or other drivers.

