## Hypotheses

The hypotheses being tested are

1. that adolescents with Osgood-Schlatter, has a lower knee extension RTD in their affected knee compared to matched controls
2. that adolescents with Osgood-Schlatter, has a lower knee extension RTD in their affected knee compared to their potential asymptomatic knee
3. that adolescents with Osgood-Schlatter, has a lower knee extension RTD in their potential asymptomatic knee compared to matched controls
4. that adolescents with Osgood-Schlatter, has a lower knee flexion RTD in their affected knee compared to matched control
5. that adolescents with Osgood-Schlatter, has a lower knee flexion RTD in their affected knee compared to their potential asymptomatic knee
6. that adolescents with Osgood-Schlatter, has a lower knee flexion RTD in their potential asymptomatic knee compared to matched controls
7. That levels of either early or late rate of torque development is negatively correlated with pain during rate of torque development-testing, countermovement jump height or power, anterior knee pain provocation test score, current pain, pain duration, KOOS child 'Pain', 'Sport/rec' or 'QoL' subscales,

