## Statistical methods

The outcome variables (rate of torque development 0-100 ms, 0-200 ms, peak RTD, time to peak RTD, time to peak torque for both knee extension and knee flexion, respectively) will be compared between groups using an unpaired two-sided students t-test, assuming the residuals will be normally distributed, otherwise the non-parametric alternative, the Wilcoxon rank sum test, will be used. The alfa and beta-1 level will be set for 5% and 80%, respectively.

As outcome variables have been a priori specified and prioritized, and also analyzed and reported in the pre-specified order, no corrections for multiple testing will be applied. Data will be reported with between-group differences, standardized effect sizes based on Cohens d, exact p-values, and 95% confidence intervals. All data inspection, analysis, and visualizations will be conducted using R (R Foundation for Statistical Computing, Vienna, Austria), in the jamovi interface (The jamovi project 2023, version 2.4.1). All r-code and full data set will be shared with journal publication or in an open-access repository.

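### The affected leg is always tested first, so in case data alone the within-case knee comparisons (hypotheses 2 and 5) cannot separate leg status from test position, and no paired or control-corrected analysis is planned

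*Combined protocol and SAP*

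**What the plan says.** All references are to the combined protocol and SAP.

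- **Knee extension (Test protocols).** The leg order is fixed: "The affected leg is tested first in each movement". One coin toss sets the order of the two movements. A second chooses a nominal index leg in controls: "In the control group the affected leg will be decided by coin toss". No coin toss sets which leg a case starts with. Each participant has two practice trials, and the leg is supported "to allow full rest between trials, lasting 1-minute". No rest between legs is stated.
- **Hypotheses.** Hypothesis 2 is that cases have "lower knee extension RTD in their affected knee compared to their potential asymptomatic knee"; hypothesis 5 is that they have "lower knee flexion RTD in their affected knee compared to their potential asymptomatic knee". The word potential implies that some cases may have no asymptomatic knee.
- **Statistical methods.** Outcomes "will be compared between groups using an unpaired two-sided students t-test", with the Wilcoxon rank sum test as fallback. There is no paired test, no term for test position, and no use of the controls' first-versus-second leg difference.
- **Aim.** The question is whether rate of torque development (RTD) "is reduced in the asymptomatic limbs or during knee flexion in adolescents with Osgood-Schlatter, compared to a matched group of asymptomatic adolescents". The within-case comparison is part of neither the aim nor the main interest given under Expected results and implications.

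**The concern.** In every case with one affected knee, the affected knee is measured first and the asymptomatic knee second. Any systematic difference between first and second position therefore adds to the leg difference. Learning or warm-up would raise the second leg and exaggerate the deficit in the affected knee. Fatigue or carry-over would lower the second leg and hide a deficit. No analysis confined to the cases can tell these apart from a true leg difference.

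The plan also lacks an analysis suited to hypotheses 2 and 5. Someone filling that gap would probably choose a paired t-test in cases, which handles the pairing but keeps the confounding. At stake is whether a result for these two hypotheses can be attributed to the condition. The sample size and the comparisons with controls are not at stake in the same way.

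**Working it through.** **1. The plan's own figure.** Inputs from Sample size: difference 3 (6 versus 3), SD 2.6, two-sided 5%, power 80%. The two-sample t-test needs n = 12.83, so 13 per group, with power 80.6%. The figure reproduces. It covers the between-group comparison only; no size is given for hypotheses 2 and 5.

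**2. Is the leg effect identifiable?** For cases, the first-minus-second difference estimates (leg effect + position effect): one quantity for two unknowns. For controls it estimates the position effect alone, because their index leg is chosen by coin toss and they have no affected knee. Subtracting the control difference isolates the leg effect, provided the position effect is the same in both groups.

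**3. Assumptions for sizing.** None of these is in the documents: position shift 0.6 Nm/kg/s (10% of 6) or 0.3 (10% of 3), between-knee correlation ρ of 0.5 to 0.8, and 10 of the 13 cases with one affected knee. The SD of 2.6 is the plan's.

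**4. Formulas** (noncentral t, two-sided 5%).
- SD of a within-person difference: s = 2.6·√(2(1−ρ)) = 2.60, 2.01, 1.64 at ρ = 0.5, 0.7, 0.8.
- Paired test in cases: SE = s/√10, 9 df. At ρ = 0.5, SE = 0.822 and a shift of 0.6 gives noncentrality 0.73. At ρ = 0.8, SE = 0.520 and noncentrality is 1.15.
- Case-minus-control contrast, 10 versus 13: SE = s·√(1/10 + 1/13) = 0.421·s, 21 df.
- Counterbalanced order with a position term, cases split 5-5: SE = (s/2)·√(1/5 + 1/5), 8 df.
- Unpaired t-test on the two legs of the same 10 cases: simulated, 200,000 runs.

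| | ρ = 0.5 | ρ = 0.7 | ρ = 0.8 |
|---|---|---|---|
| False positives, paired in cases, shift 0.3 | 6.2% | 7.1% | 8.1% |
| False positives, paired in cases, shift 0.6 | 10.0% | 13.5% | 17.9% |
| False positives, unpaired, shift 0.6 | 2.7% | 1.1% | 0.6% |
| Power at true 1.5, paired, no shift | 37% | 56% | 73% |
| Power at true 1.5, paired, opposing shift 0.6 | 17% | 24% | 34% |
| Power at true 1.5, unpaired, no shift | 17% | 13% | 11% |
| Power at true 1.5, case-minus-control contrast | 26% | 39% | 54% |
| Power at true 3, case-minus-control contrast | 74% | 92% | 99% |
| Power at true 1.5, counterbalanced, position term | 36% | 54% | 72% |

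At a true difference of 3, the paired test in cases has power 90% to 99.9% without a shift and 74% to 98% with an opposing shift of 0.6.

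**5. What the contrast does and does not remove.** A shift common to both groups cancels, so false positives return to 5%. A shift of 0.6 in cases only does not cancel: false positives are 8% to 13%.

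**6. Comparisons with controls.** If the affected knee is set against the control's index leg, and the asymptomatic knee against the other leg, both sides share the same position and a common order effect drops out of hypotheses 1, 3, 4 and 6. If hypothesis 3 or 6 instead used the control's first-tested leg, a 0.6 shift would give 8.7% false positives (13 versus 13).

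**7. Effect of counterbalancing on the affected-knee comparison.** Mixing positions adds a variance of shift²/4. With a 10% order effect, 2.6² + 0.6²/4 = 6.76 + 0.09 = 6.85, and power goes from 80.6% to 80.1%. With 20%, 6.76 + 1.2²/4 = 7.12, and power is 78.5%.

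**The case against.** The strongest reply has four parts.

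- **The inflated error rate belongs to a test the plan does not name.** This stands. A reader might infer from the fixed order that the planned analysis rejects too often. Under the assumed shifts it does not: the unpaired test on two legs of the same cases stays under 3%. Its fault is lost power, and a paired test would be missing under any leg order. The 6% to 18% describes the natural repair.
- **The order-effect inputs are assumed.** This stands too. The documents give no position effect, no between-knee correlation and no count of one-sided cases. The practice trials and the 1-minute rest should also make learning and fatigue smaller. They do not separate whatever remains from leg status. The confounding is a fact of the design; its impact is not known.
- **The comparisons that matter are already protected.** Largely so. A reader might infer that the order rule undermines the main interest, a deficit in asymptomatic limbs. The documents do not support that: controls follow the same order, and like-with-like pairing of legs is the natural reading. What is missing is a sentence naming the control leg.
- **Carry-over specific to cases could mimic a central deficit.** It could contribute, but nothing in the documents sizes it. Expected results and implications already attributes such a deficit to causes "due to other factors than local tissue pathology, such as pain chronicity, central muscle inhibition, or other drivers", so the interpretation is not closed.

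**Conclusion.** The point holds as a cheap improvement that ranks below any issue in the case-control comparisons. Hypotheses 2 and 5 are stated, but in case data alone leg status coincides with test position, and the plan gives them neither a paired analysis nor a correction using the controls. That conclusion is structural and needs no assumed number.

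The size is a sensitivity range only. A paired test in cases would reject falsely in about 6% to 18% of studies if the second leg gained 0.3 to 0.6 Nm/kg/s, with SD 2.6, correlation 0.5 to 0.8 and 10 one-sided cases. An opposing effect would cost power instead, and the direction is unknown. For hypotheses 3 and 6 the remaining point is a clarification, since common order effects cancel when corresponding legs are compared.

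**What to change.** **If testing has begun** (the summary Methods schedule data collection for February to May 2023), keep the order. Analyse hypotheses 2 and 5 as the first-minus-second leg difference in cases minus that in controls: a group-by-position contrast with participant as a random effect. State that this removes a position effect common to both groups but not one specific to cases. It needs no new data. The price is lower power: 26% to 54% at a true 1.5 and 74% to 99% at a true 3, under the assumptions above.

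**If testing has not begun**, counterbalance leg order in both groups from a list held by the unblinded examiner, record test position, and use a paired model with a position term. This costs one list at unchanged sample size, one degree of freedom in the within-case analysis, and a small loss in the affected-knee comparison (80.6% to 80.1% at a 10% order effect; 78.5%, below the planned 80%, at 20%).

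Counterbalancing reduces but does not remove carry-over from the affected to the asymptomatic leg. If carry-over c acts only on an asymptomatic leg tested second, the within-case contrast is shifted by c under the fixed order and by c/2 under a balanced one. Comparing asymptomatic legs tested first with those tested second then gives some information on c.

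**In either case**, state that the comparator for hypotheses 3 and 6 is the control's non-index leg, which is the second-tested leg if the order is kept. This costs one sentence.

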#### Anterior knee pain provocation test

The anterior knee pain provocation test is a unilateral self-performed and self-rated test, designed to provoke known anterior knee pain. Only the affected or most affected knee is tested. In the control group, the “affected leg” is decided by coin toss.

The participant will be instructed to *stand on the affected leg, with the non-affected side against the wall, and their back straight*. The back of the hand is held against the wall as support. They will then be instructed to stand in a static single-legged squat position, with knee flexion about 60°, while the other leg is extended forward above the ground. The position is held for 45 sec and timed with a stopwatch. Standardized verbal instruction is provided before each trial by the tester: *are you ready to start the test? Start... and stop.*

Participants will provide their perceived pain intensity immediately before and after completing the 45s. hold.

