### Descriptive variables

Variables collected for descriptive purposes are data on examination findings, pain intensity and duration, Peak Heigh Velocity, level of sports participation and anthropometrics

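### Control index leg is set by coin toss, case index leg by disease, and leg dominance is never recorded, so a modest, uncheckable bias can enter the limb comparisons

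*Combined protocol and SAP*

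**What the plan says.** The section Knee extension fixes the order of the legs, "The affected leg is tested first in each movement", and then defines the index leg for controls: "In the control group the affected leg will be decided by coin toss". The section Anterior knee pain provocation test uses the same toss for controls. For cases it says: "Only the affected or most affected knee is tested". That is the only place where the index knee of a bilaterally affected case is defined.

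Hypothesis 1 states that a case "has a lower knee extension RTD in their affected knee compared to matched controls". Hypothesis 3 states that a case "has a lower knee extension RTD in their potential asymptomatic knee compared to matched controls". Hypotheses 4 and 6 repeat these two contrasts for flexion, and hypotheses 2 and 5 compare the two knees of the same case. None of the between-group hypotheses names the control limb.

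Study design matches the groups on sex, age and type of sport. Descriptive variables ends its list with "level of sports participation and anthropometrics". Neither that list nor Patient Reported Outcome Measures or Outcome measures names the dominant or preferred leg. Statistical methods specifies an unadjusted two-sample t-test or a Wilcoxon rank sum test.

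Movement order is also tossed: "The order of the movements is decided by coin" toss, with no balancing within groups.

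**The concern.** The two groups obtain their index legs by different mechanisms. A fair coin makes the index leg dominant in half of controls on average. In cases the knee that became painful decides, and nothing in the documents says that this happens equally often on both sides.

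Suppose affected knees were mostly dominant legs and dominant legs developed torque faster. Affected case knees would then be compared with too few dominant control legs, which masks part of a local deficit (hypotheses 1 and 4). Asymptomatic case knees would be compared with too many dominant control legs, which imitates part of a deficit (hypotheses 3 and 6).

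The second error is the more awkward one. Expected results and implications names reduced values in non-symptomatic limbs or in flexion as the main interest, and would read them as a sign of central inhibition. Without a record of dominance, this rival explanation can be neither checked nor adjusted for, even from the shared data set.

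**Working it through.** **The plan's own figure.** From Sample size: means 6 v 3 (difference 3), SD 2.6, two-sided alpha 5%, power 80%. The two-sample t-test (noncentral t) gives n = 12.83 per group, rounded up to 13, with power 80.6% at 13. The stated sample size reproduces and is not in dispute.

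**Direction.** Let p be the share of cases whose affected leg is dominant, and d the dominant minus non-dominant difference in rate of torque development. The expected dominant share in controls is 0.5. This holds whether the index leg, the other leg or the mean of both is used, so the unnamed control limb does not change the result.

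- Affected knee v control (hypotheses 1, 4): bias in case minus control = pd − 0.5d = (p − 0.5)d.
- Asymptomatic knee v control (hypotheses 3, 6), unilateral cases: (1 − p)d − 0.5d = −(p − 0.5)d.
- Within case (hypotheses 2, 5): pd − (1 − p)d = (2p − 1)d. No control leg enters this contrast.

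**Size.** Neither p nor d is in the documents. Assumptions: d = 5% to 15% of the plan's 6 Nm/kg/s, so 0.05 × 6 = 0.30 to 0.15 × 6 = 0.90; p = 0.5 to 0.9. Power is for a true deficit of 3. Rejection is two-sided, for no true deficit in the asymptomatic limb. Both use SD 2.6 and 13 per group.

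| d | p | bias, hyp. 1 | bias, hyp. 3 | power, hyp. 1 | rejection, hyp. 3 |
|---|---|---|---|---|---|
| any | 0.5 | 0 | 0 | 80.6% | 5.0% |
| 0.30 | 0.7 | +0.06 | −0.06 | 79.0% | 5.0% |
| 0.90 | 0.7 | +0.18 | −0.18 | 75.6% | 5.3% |
| 0.30 | 0.9 | +0.12 | −0.12 | 77.3% | 5.1% |
| 0.90 | 0.9 | +0.36 | −0.36 | 70.0% | 6.3% |

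The largest value is 0.4 × 0.90 = 0.36 Nm/kg/s. That is 0.36/6 = 6% of the assumed control mean, 0.36/3 = 12% of the planned difference and 0.36/2.6 = 0.14 SD. For p below 0.5 every sign reverses: at p = 0.3 and d = 0.90 the bias is −0.18 in hypothesis 1 and +0.18 in hypothesis 3.

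**Movement order.** With independent fair tosses in 13 and 13, the number tested extension-first differs between groups by 3 or more with probability 33%, and by 4 or more with probability 17%. The toss is independent of group, so these are probabilities of chance imbalance and not a bias.

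**The case against.** Much of the case for leaving the plan alone is sound. The toss is an unbiased choice within controls. If p = 0.5 or d = 0 there is no systematic error, and the documents give no reason to prefer any other value. The questionnaire content is described partly by example, so the preferred leg might be asked in practice, although no section says so. Even at the top of the assumed range the error is small against a planned difference of 50%.

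Four stronger conclusions are tempting, and the documents do not support them.

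- A reader might infer that the toss manufactures a deficit in the asymptomatic limb. The worst case shown lifts false rejection only from 5.0% to 6.3%, and the sign depends on an unknown p.
- A reader might take hypotheses 3 and 6 as an exact mirror of 1 and 4. That holds for unilateral cases only. Bilateral cases, which the wording of the hypotheses and of the provocation test allows for, enter hypothesis 1 but have no asymptomatic knee for hypothesis 3, so p can differ between the two sets.
- A reader might blame the toss for the within-case bias of (2p − 1)d, which is twice as large. That bias involves no control leg and no change to the toss removes it.
- A reader might count the movement-order imbalance as bias. It is part of ordinary random error, and no order effect can be sized from the documents.

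What remains is that dominance is neither recorded, matched nor adjusted for, so the plan cannot show that p was near one half.

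**Conclusion.** The point holds as an inexpensive improvement and not as a flaw that undermines the study. The bias is (p − 0.5)d in hypotheses 1 and 4 and, for unilateral cases, the opposite in 3 and 6. Under the stated assumptions it runs from 0 to 0.36 Nm/kg/s in either direction, and it costs hypothesis 1 at most about 10 points of power (80.6% to 70.0%).

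It deserves attention chiefly because of hypothesis 3. The plan states no expected effect for the asymptomatic limb, so an error of a few per cent of the mean may matter more there than against the 50% difference used for sample size. The Nm/kg/s figures rest on the plan's assumed control mean of 6 and SD of 2.6 for early rate of torque development. Applying the same percentage range to flexion is a further assumption.

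**What to change.** (a) Ask every participant, case and control, for the preferred leg at the existing telephone screen.

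(b) Let the unblinded examiner assign control index legs so that the group-level share of dominant index legs follows the case share, for example by a toss weighted by the running case share. No control should be required to follow or copy a particular case. Such a sequence would give the blinded tester information about status, tie group to calendar time, and fit poorly with group-level matching and the replacement of excluded participants. The alternative is to keep the fair toss and, as a sensitivity analysis, use the bilateral control data to form a control mean standardised to the case dominance mix: p̂ × dominant-leg mean + (1 − p̂) × non-dominant-leg mean, with the weights swapped for the asymptomatic-knee comparison and p̂ taken from the cases in that comparison. Because the index leg is always tested first, the weighting is best done within testing position.

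(c) Report dominance of the index leg by group, and add it as a limb-level term in a sensitivity analysis of hypotheses 2 and 5. The term can be estimated only if some cases are affected on each side.

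(d) Replace the movement-order toss by a concealed 7/6 list within each group, with the same movement in the majority in both. This removes chance imbalance only.

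The cost is one screening question, a list kept by the unblinded examiner and one extra sensitivity analysis. Sample size, outcomes and primary tests are unchanged.
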